## 1.0 Research Introduction

### 1.1 Purpose/Specific Aims

The purpose of the current investigation is to examine strategies for encouraging smokers at socioeconomic disadvantage in New Brunswick, New Jersey to quit in a randomized clinical trial. Tobacco use is a substantial problem for individuals at socioeconomic disadvantage (SED). While smoking prevalence has decreased across the United States over the past several decades, this decrease has not occurred at all levels of socioeconomic status. Those at lower socioeconomic status smoke at higher rates than those at higher socioeconomic status (Tucker-Seeley et al., 2015).

#### A. Objectives

In order to examine strategies for encouraging smoking cessation in socioeconomically disadvantaged smokers, we will randomize self-identified smokers interested in our study to one of three intervention conditions: (1) Brief motivational interviewing (MI) and referral to the NJ quitline and local Tobacco Dependence Program, (2) provision of a two-week supply of nicotine replacement patch and nicotine lozenge (NRT sampling) and referral to the NJ quitline and local Tobacco Dependence Program, or (3) referral only. This randomized controlled trial will allow for a direct comparison of three brief and easy to implement treatment conditions in relation to various cigarette smoking outcomes.

#### B. Hypotheses / Research Question(s)

Brief advice to quit (i.e., referral), brief motivational interviewing, and nicotine replacement therapy are recommended approaches to promote smoking cessation and reduce health disparities in low-income smokers (Fiore et al., 2008). However, as compared to referring participants to the NJ Quitline, we expect brief MI and provision of NRT to be superior in terms of: (1) Increasing motivation to quit; (2) increasing self-efficacy to quit; (3) setting a quit date; (4) making a cessation attempt; (5) and achieving initial abstinence.

### 1.2 Research Significance (*Briefly describe the following in 500 words or less*):

A disproportionate number of individuals who use tobacco are from low socioeconomic status (Tucker-Seeley et al., 2015). By reaching smokers at socioeconomic disadvantage who may not initially be interested in seeking cessation services and prompting quit attempts in this population, we can have a positive impact on public health.

Brief motivational interviewing is a psychosocial intervention designed to promote behavioral change and recommended as part of the clinical practice guidelines for smoking cessation (Fiore, 2008), in particular for populations with low motivation to quit. This intervention assumes clients are motivated and have the ability to quit. By avoiding direct advice or convincing, the therapist carefully uses a series of techniques to illicit intrinsic motivation from the client to change. Although MI presumably is designed to affect motivation, thereby eliciting behavioral change, mechanisms research does not support this relationship and instead suggest that a therapist's ability to engage the client in 'change talk,' i.e., talk about what it would look like to engage in different behaviors, is central to a favorable outcome. Whereas meta-analytic reviews of MI indicate relatively small effect sizes, a recent meta-analytic review that examined the combined effect of brief MI (i.e., <60 minutes) found that it was significantly related to long-term cessation ( $d=.33$ ). A similar significant effect for follow-up was found that MI that was not combined with pharmacotherapy ( $d=.21$ ).

Clinical practice guidelines additionally recommend the provision of NRT to enhance smoking cessation (Fiore et al., 2008) via reduction in nicotine withdrawal. Meta-analytic reviews generally provide support for the efficacy of NRT in promoting cessation, but are somewhat mixed. More recently, combination NRT is emerging as a preferred method that provides smokers with constant nicotine replacement (e.g., via the nicotine patch) as well as relief for 'breakthrough' cravings via the addition of gum or lozenge (Carpenter et al., 2013).

### 1.3 Research Design and Methods

Protocol version: 03.15.2019

PI Name: [name].

Protocol Title: Addressing Tobacco Among  
Public Housing Residents

3

RESERVED FOR IRB STAMP

DO NOT MODIFY THIS SPACE

IRB ID: Pro20170000679

IRB Form Version: y120116

3/25/2019

Expiration Date:

3/24/2020

**Overview:** We will conduct a pilot randomized clinical trial in which socioeconomically disadvantaged smokers receiving services at a New Brunswick, NJ based agency (e.g., New Brunswick Housing Authority (NBHA) or Elijah's Promise) are randomized to one of two brief interventions designed to enhance motivation to quit smoking (see Study Interventions below) or to a control group. Participants will be re-contacted at one-month by a research assistant who is blind to the condition to which the participant was allocated to assess number of quit attempts and abstinence from cigarettes.

**Participant Recruitment and Screening:** In collaboration with staff at the New Brunswick, NJ based community partners, we will use flyers to advertise and will recruit daily smokers receiving services at a New Brunswick, NJ based agency. Interested participants will complete a brief in-person or telephone screening where they will be assessed by trained study personnel who will determine initial eligibility. Participants must be between the age of 19 and 65, must self-report being a daily smoker and provide biochemical verification of smoking status (expired breath carbon monoxide reading >5). Assessing carbon monoxide to verify smoking status is a common approach in tobacco use studies.

### **1.3.1 Biochemical verification**

To confirm smoker status, expired breath carbon monoxide (CO) levels (also commonly collected in tobacco dependence treatment studies) will be assessed with a carbon monoxide monitor and CO reading in parts per million (ppm) will be recorded. The carbon monoxide monitor used will be the Bedfont Scientific Ltd. Micro+ Smokerlyzer. The Micro+ Smokerlyzer is a hand-held, battery powered instrument which uses electrochemical technology to sample the gas and a microprocessor to convert the output from the sensor to a carbon monoxide (CO) concentration. The result and menus are displayed on a color LCD and an accompanying buzzer sounds in response to the CO level. The instrument is controlled using a touch screen operation and has a USB link to a computer to download readings.

The Micro+ uses a breath sampling D-Piece with integrated bacterial and viral filter and a one-way valve designed to maximize infection control. Each patient uses a fresh mouthpiece for each breath sample. The D-Piece may be reused or replaced as required.

The patient is asked to hold their breath for a 15 second countdown. This is displayed on the screen of the device. At the end of the breath hold, the patient blows gently into the Micro+ expiring as much of the breath in their lungs as possible. The reading on the device shall rise until the peak reading is held on the display.

A research assistant will provide instructions on how to use the CO monitor and will record the results at visit 1 and one-month follow-up appointments. The study PI is accountable for the device.

Exclusion criteria include taking FDA approved smoking cessation or anti-psychotic medications, self-reported medical issues of potential concern to nicotine replacement therapy users (i.e., unstable angina pectoris, myocardial infarction, or significant cardiac arrhythmia (including atrial fibrillation) in the past 30 days), or self-reported pending legal issues with potential to result in incarceration. Additionally, women must state in writing that they are not pregnant or nursing, planning on becoming pregnant in the next two months, and that they are using effective birth control.

**Visit 1:** Following the initial phone screen study staff will arrange to meet with eligible participants to administer additional measures as well as the brief intervention. In addition to verifying inclusion/exclusion criteria as well as smoking status, participants will be asked to complete a questionnaire battery online using a laptop provided by study staff, and a brief interview to further assess motivation and confidence to quit, substance use, physical health, and mental health status and history, as well as smoking cessation history.

**Study Interventions:** Next, we will use a block randomization procedure to allocate participants to one of three groups: A *single session motivational intervention (MI)*, which will include a 30-minute therapy session designed to enhance motivation to quit smoking, followed by a referral to the NJ State Quitline and local Tobacco Dependence Program; (2) An *NRT sample intervention*, which will include free two-week supplies of nicotine patches and nicotine lozenge with instructions for proper use and a referral to the NJ State Quitline and local Tobacco Dependence Program, or (3) An *assessment and referral only control*.

Block randomization is a procedure in which participants are randomly allocated to intervention groups within blocks such that an equal number are assigned to each intervention. We will use the Sealed Envelope Ltd. 2017 application to electronically develop a list of 60 allocation outcomes using a block randomization procedure with 3 intervention groups and block sizes of 3, 6, and 9. The study coordinator will use this list to inform study therapists of the intervention to which participants were assigned.

Upon completion of the intervention, participants will be scheduled for a one-month follow-up visit with a research assistant. Participants will be reminded of their appointment via text, phone, and email 48 and 24 hours prior.

**One-month Follow-up:** Participants will be asked to complete a brief online survey once again, and smoking status will be verified via self-report and carbon monoxide analysis of breath sample. Staff will also conduct brief interviews to assess main outcomes of interest.

#### **1.4 Preliminary Data**

Drs. [name] and [name] have committed their academic careers to research on tobacco use and dependence. In addition to academic research, [name] was Director of the Mercer County Tobacco Program from 2005–2010 where in addition to providing smoking cessation services, he partnered with community organizations in Mercer County to increase awareness of the consequences of smoking and to increase the uptake of tobacco dependence treatment services.

[name] recently published data on a motivational interviewing intervention ([name] et al., 2016) similar to the one proposed in the current application in which he found smokers with schizophrenia receiving a single-session motivational interviewing intervention were significantly more likely than those receiving an educational intervention to make a quit attempt. In addition, [name] recently published research indicating that clinical management of nicotine withdrawal of severely mentally ill smokers on smoke-free inpatient units is enhanced by offering NRT directly upon admission; these findings support the exploration of our NRT in smokers who live in newly smoke-free public housing units.

### **1.5 Sample Size Justification**

We have a target N of 60 smokers (n=20/treatment condition). In terms of race/ethnicity, we anticipate our sample will be reflective of cigarette smokers living in the greater New Brunswick, NJ area: We expect to enroll two participants weekly in order to meet our target N. Estimating that 50% of the sample will make quit attempt during the course of the study, our main outcome of interest, this is adequate to group differences with 95% confidence (CI: 0.38, 0.61).

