**6.0 Research Data Protection and Reporting**

**6.1 Data Management and Confidentiality**

**A.** Success of randomization will be checked via summary statistics of baseline demographic and psychosocial characteristics. Depending on the measurement scale of each variable, we will use either  $\chi^2$  or independent samples t-tests, corrected for unequal variances if indicated. Variables found to show significant baseline differences between groups will be included as covariates. Logistic regression analyses will be conducted to examine differences in dichotomous outcomes such as abstinence (yes/no), quit attempts (yes/no), and treatment seeking (yes/no). Because this is a small, pilot study, we will report effect sizes representing each of the two active interventions (MI and NRT sampling) as compared to the control intervention (referral only).

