**B. Provide a power analysis. (As applicable, e.g. quantitative research).**

N/A. This is a small, pilot study. We will use the data collected in this study to estimate effect sizes for a larger NIH grant application.

**C. Describe the steps that will be taken to secure the data (e.g., training, authorization of access, password protection, encryption, physical controls, certificates of confidentiality, and separation of identifiers and data) during storage, use, and transmission.** The link between participants to their study ID will be stored in a password-protected file, located within a password-protected database on an encrypted computer. Only select trained laboratory personnel will have access to the file. All computer files or printed data used for analysis also

will be de-identified. Consent forms and payment forms will be stored in a locked file cabinet separate from data in an office (of Division of Addiction Psychiatry, [name]) that is locked when not occupied. All research personnel will complete CITI Human Subjects Research training and pass the CITI quizzes.

Additionally, we will obtain a Certificate of Confidentiality from the NIH

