Official Title: Addressing Tobacco in Public Housing Residents

Identifiers: NCT03620708

Document Date: September 27, 2019

Statistical Analysis Plan

To assess for differences in outcomes between groups we will use chi-square for dichotomous outcomes and analysis of variance / analysis of covariance for continuous outcomes. We will consider covariates based on theoretical grounds (e.g., baseline cigarettes per day, baseline motivation to quit, financial disadvantage) and significant differences between groups at baseline. Significant results will be probed using Dunnett's method, whereby our comparison of interest was between the treatment conditions and control condition. We will further report effect size estimates (i.e., f for ANOVA; Cramer's V for chi-square) to help elucidate aspects of the pilot study that may be most beneficial. Data will also be examined based on the assumption of 'missing equals smoking' and carrying the last observation (i.e., baseline data) forward, as a relatively conservative means of handling data for the n=5 participants lost to follow-up. We will refer to additional analyses of imputed data as intent-to-treat (ITT) analyses.

Outcome 1: A self-described "serious" attempt to quit smoking cigarettes since the initial study appointment, measured by the "Quitting Preparation and Actions Questionnaire."

We will use chi-square analysis to examine differences in proportion of the participants randomized to receive the three intervention groups with respect to making a serious quit attempt between the initial appointment and the 1-month follow-up period.

Outcome 2: Self-reported contact with one of two treatment referrals provided at intervention since the time of the initial study appointment

We will use chi-square analysis to examine differences in proportion of the participants randomized to receive the three intervention groups with respect to seeking treatment at either the NJ QuitLine or a NJ Quitcenter (local tobacco dependence treatment clinic) between the initial appointment and the 1-month follow-up period.

Outcome 3: Self-reported cigarettes smoked per day

We will use Analysis of Covariance (ANCOVA) to examine differences in cigarettes smoked per day at the 1-month follow-up between participants randomized to the three intervention groups. Baseline cigarettes smoked per day and measures of motivation to quit will be included as covariates.

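### Section 1.5 claims adequacy for group differences from a confidence interval that fits only one pooled proportion; at 20 per arm and 50% quit attempts, each active-versus-control difference is known to about ±0.28 to ±0.35.

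*Protocol*

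**What the plan says.** Protocol section 1.5 sets the size: "We have a target N of 60 smokers (n=20/treatment condition". It makes one assumption about the outcome, for the sample as a whole: "Estimating that 50% of the sample will make quit attempt during the course of the study". From this it concludes, of quit attempts: "our main outcome of interest, this is adequate to group differences with 95% confidence (CI: 0.38, 0.61". It gives no arm-specific rates, no difference to be detected or estimated, no power, and no interval for a difference.

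Elsewhere the interest is in contrasts between arms. Protocol section 6.1A says: "Because this is a small, pilot study, we will report effect sizes representing each of the two active interventions (MI and NRT sampling", each set against referral only. The SAP states that "our comparison of interest was between the treatment conditions and control condition", to be probed by Dunnett's method. For Outcome 1 it plans a chi-square test across participants "randomized to receive the three intervention groups with respect to making a serious quit attempt".

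Protocol section 6.1B marks the power analysis as not applicable because this is a small pilot, and adds: "We will use the data collected in this study to estimate effect sizes for a larger NIH grant application".

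**The concern.** The only figure in either document for what 60 participants can show on quit attempts is an interval for the wrong quantity. It describes how well the overall quit-attempt rate would be known, yet it is offered as support for adequacy on group differences.

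The sentence has lost its verb, so the intended claim is unclear. If detecting differences was meant, it conflicts with section 6.1B, which disclaims power. If estimating them was meant, the interval is still not that of a difference.

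The effect sizes are meant to inform a larger grant application, so their uncertainty is central to the purpose of the pilot. A reader who takes ±0.115 as the precision of the arm comparison would put too much trust in the point estimates. The same reader could take a non-significant chi-square as evidence of no effect.

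**Working it through.** **Inputs.** From section 1.5: N = 60, 20 per arm, quit-attempt rate 0.50, 95% confidence, stated interval 0.38 to 0.61. From section 4.5A: a total of 64. From section 6.1A and the SAP: two contrasts, each active arm against control, with Dunnett's method. From the SAP: five participants lost to follow-up. Assumptions made here: 0.50 in each arm, all 20 per arm analysed, and a large-sample Dunnett critical value of 2.212 (two contrasts with one control, correlation 0.5).

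**1. The plan's own interval.** Its half-width is (0.61 − 0.38)/2 = 0.115. At p = 0.5 the Wilson half-width is z / (2√(n + z²)), with z = 1.96 and z² = 3.84.

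| Reading | Calculation | 95% interval |
|---|---|---|
| Pooled, 30/60 | 1.96/(2√63.84) = 0.123 | 0.377 to 0.623 |
| Pooled, 32/64 | 1.96/(2√67.84) = 0.119 | 0.381 to 0.619 |
| Two arms, 20/40 | 1.96/(2√43.84) = 0.148 | 0.352 to 0.648 |
| One arm, 10/20 | 1.96/(2√23.84) = 0.201 | 0.299 to 0.701 |

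For 30/60, Wald gives 0.373 to 0.627 and the exact method 0.368 to 0.632. The stated interval is therefore that of one proportion in about 60 people. The match is approximate, since no standard method at N = 60 rounds to exactly 0.38 to 0.61. Wilson gives 0.38 to 0.62. The upper limit of 0.61 may be a truncation, or may come from N = 64 with truncation; this is minor. An interval for a difference between equal rates would centre on 0, not near 0.5.

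**2. Active versus control, 20 per arm, 0.50 in both.**
- Wald: 1.96 × √(2 × 0.25/20) = 1.96 × 0.158 = 0.310.
- Newcombe (two Wilson half-widths combined): √(0.201² + 0.201²) = 0.284.
- Wald with Dunnett: 2.212 × 0.158 = 0.350.
- Newcombe with Dunnett: Wilson half-width 2.212/(2√(20 + 4.89)) = 0.222, times √2, gives about 0.31.

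Relative to the stated half-width: 0.284/0.115 = 2.5 and 0.350/0.115 = 3.0.

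**3. Arm size needed for a half-width of 0.115 on a difference.** n = 2 × 0.25 × (1.96/0.115)² = 0.5 × 290.5, or about 145 per arm.

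**4. Sensitivity to the assumptions.**
- Both rates at 0.20: 1.96 × √(2 × 0.16/20) = 0.248, still more than twice 0.115.
- The five losses spread evenly (an assumption), 55/3 = 18.3 per arm: Wald 1.96 × √(0.5/18.3) = 0.324, and 0.365 with Dunnett.

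**5. What could be detected, if that was meant.** These figures come from exact enumeration with 20 per arm and a two-sided 5% level.
- Two-group chi-square, unadjusted: 80% power needs 50% v 89%, or 28% v 72%.
- The SAP's three-group chi-square (2 df, critical value 5.991), overall rate held at 50%: 80% power needs about 23% v 64% v 64%, a gap of 41 points. Power is 49% for 30% v 60% v 60%, and 24% for a 20-point gap (36.7% v 56.7% v 56.7%).

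**The case against.** The strongest reply is that the documents already disclose this in substance. Section 6.1B says that there is no power analysis, section 6.1A and the SAP both speak of a pilot, and no test, sample size or outcome depends on the sentence in section 1.5. An interval that directly follows a 50% rate can also be read naturally as the interval for that 50%, in which case the factor of 2.5 to 3 compares two different quantities. This lowers the severity. It does not rescue the sentence, which ties the interval to group differences, and section 6.1B leaves that contradiction in place.

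A second reply is that the range depends on conditions. That is true. It moves with the quit-attempt rates and the losses, from about ±0.25 to ±0.37 in the cases worked above. The SAP uses Dunnett's method only to probe significant results and does not say how it applies to a chi-square outcome, so the adjusted figures rest on an assumed critical value. The range should always be given with its conditions. None of these cases comes near ±0.115.

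A third reply concerns the remedy. The documents plan Cramer's V and logistic regression, not a risk difference, and the SAP already reports five losses, so a planning interval would soon be superseded by observed ones. This stands as a reason to put confidence intervals around the reported effects as well. The SAP does not currently ask for them.

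**Conclusion.** The concern holds. The interval in section 1.5 belongs to a pooled proportion of 50% in about 60 people and does not support any claim about differences between arms, whether detection or estimation was meant.

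With 50% in each arm and 20 per arm analysed, each active-versus-control difference has a 95% half-width of 0.28 to 0.31 unadjusted, and 0.31 to 0.35 with an assumed Dunnett value of 2.21. The stated ±0.115 is smaller by a factor of 2.5 to 3. Loss to follow-up widens the interval, and rates far from 50% narrow it somewhat.

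The error should be corrected, but its weight is modest because the study is presented as a pilot and claims no power in section 6.1B.

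**What to change.** Remove the adequacy claim from section 1.5 and put in its place:

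> If 50% make a quit attempt, the expected 95% confidence interval is 0.38 to 0.62 overall (Wilson, 30/60), 0.30 to 0.70 within an arm (Wilson, 10/20), and about ±0.31 for each active-versus-control difference (Wald, 20 per arm; about ±0.35 with Dunnett adjustment for two comparisons). This pilot is intended to estimate effect sizes and is not powered to detect group differences.

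Carry the same statement into the SAP or the report, so that a non-significant result is not read as no effect. Because the SAP already records five losses, the report should also give a confidence interval with each active-versus-control effect, based on the numbers actually analysed.

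The cost is one replaced sentence in section 1.5, the same sentence in the SAP or report, and the added intervals in the report. Sample size, allocation, outcomes and planned tests do not change. The stated precision becomes less favourable.
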